4.2.2 Protocol Deviations

The number and percentage of participants with the following protocol deviation criteria will be summarized for each criterion and overall, by AT132 dose level and overall as well as by investigative site for all participants who were randomized. Participants deviating from a criterion more than once will be counted once for the corresponding criterion.

The unique identifiers will be as follows, and only apply to major deviations:

- PD1 - Inclusion/ Exclusion,
- PD2 - Withdrawal Criteria,
- PD3 - Study Intervention,
- PD4 - Excluded Concomitant Medications,
- PD5 - Informed Consent,
- PD6 - Safety Reporting,
- PD7 - Procedures/ Tests,
- PD8 - IRB/ Ethics Committee.

4.2.3 COVID-19 Impact

Assessments that were indicated in the eCRF as impacted by the COVID-19 pandemic will be listed.

4.2.4 Demographic and Other Baseline Characteristics

Demographic and other baseline characteristics will be summarized descriptively by AT132 dose level and overall for all randomized participants (demographics only), the FAS, and SAF analysis set.

Demographic characteristics will include age at dosing (months), age group (< 1 year, 1 – <2 years, ≥ 2 years at the time of dosing), sex (all male), race, ethnicity, and country where participant resides.

The following baseline characteristics will be summarized:

- Growth Parameters:
 - o Baseline weight
 - o Height
 - o Body mass index (BMI)
 - o Head circumference
- Disease History:
 - o Age at diagnosis of XLMTM
 - o Age when first symptoms noted
- Ventilator History:
 - o Ventilator type at baseline (invasive vs non-invasive)
 - o Hours of ventilation support at baseline (Primary endpoint)
- Genetics and Baseline Protein Expression:
 - o Category of genetic diagnosis (Nucleotide or base change, amino acid or codon change, Exon)
 - o Myotubularin expression at baseline
- Endpoints at Baseline:
 - o Motor Development Milestone assessments at baseline
 - o Liver ultrasound at baseline result
 - o CHOP-INTEND total score at baseline
 - o MIP at baseline
 - o Ability to sit unassisted ≥ 30 seconds

- Number of gross motor function milestones achieved at baseline

Medical history is coded in MedDRA, and will be summarized by System Organ Class (SOC) and Preferred Term (PT), by treatment group and overall for the SAF.

Participants genetic testing results will be listed.

4.2.5 Previous and Concomitant Medications

Previous and concomitant medications will be summarized by therapeutic subgroup (ATC 2nd level), chemical subgroup (ATC 4th level) and preferred World Health Organization (WHO) name (active ingredients for combination drugs) by AT132 dose level and overall for the SAF.

Participants taking the same medication multiple times will be counted once per medication and investigational period. A medication which can be classified into several chemical and/or therapeutic subgroups is presented in all chemical and therapeutic subgroups.

Previous medications are defined as medications that participants started prior to administration of study drug. Concomitant medications are defined as any medications that participants took on or after the date of administration of study drug and through the end of follow-up.

Medications that started prior to and continued after administration of study drug will be counted in both previous and concomitant medications.

4.2.6 Glucocorticoid Administration

Concomitant glucocorticoid administration will be summarized by AT132 dose level and overall for the SAF. Glucocorticoids will be identified by ATCr_CD = "H02AB".

The glucocorticoid administration summary will include a summary table of:

- Duration of Taper
- Total days on protocol-specified glucocorticoid dose regimen (For subjects weighing < 60 kg, the dose will be 1 mg/kg prednisolone orally daily and for subjects weighing ≥ 60 kg, the dose will be 60 mg prednisolone orally daily) prior to taper (day prior to taper start date – Day -1 date + 1),

The day of taper start for a participant is defined as the date of first glucocorticoid record in the concomitant medication dataset where (frequency)*(dose) is less than the (frequency)*(dose) value for the initial glucocorticoid record in the dataset.

A listing of all subjects' glucocorticoid administration will be provided.

Individual subject line plots of ALT x ULN, AST x ULN, Total Bilirubin x ULN, Direct Bilirubin x ULN, CK x ULN, serum bile acid x ULN, and Troponin T x ULN will be created, with a dashed vertical line indicating where the taper began.

A swimmer plot may be created to visualize the glucocorticoid administration progression.

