 - Key identified risks associated with AT132 administration observed in Study ATX-MTM-002 are listed below. Of the overall risks associated with rAAV gene therapy, thrombotic microangiopathy and sensory ganglionopathy have not been observed in ATX-MTM-002 study subjects. Long-term follow-up is important in understanding whether these AEs have long-term implications. Refer to the Investigator's Brochure for further details.
 - **Hepatobiliary events:** Many XLMTM patients have liver dysfunction and cholestasis, which places them at increased risk for hepatobiliary dysfunction or even hepatic failure with rAAV administration. A prospective natural history study (Study ATX-MTM-009) reported that overall, 91% of subjects had histories of hepatic

disease and/or prospectively experienced related AEs or laboratory or imaging abnormalities (Dowling, 2022).

- In Study ATX-MTM-002, SAEs due to hepatobiliary dysfunction occurred after AT132 administration and were characterized by hyperbilirubinemia, cholestatic liver dysfunction, transaminases elevations, ascites, and serum bile acid elevations. Fatal outcomes were observed in 4 subjects due to multifactorial causes including hepatobiliary failure: 1 subject who received the 1.0×10^{14} vg/kg dose and 3 subjects who received the 3.0×10^{14} vg/kg dose. All 4 subjects showed increases in direct and total bilirubin values (> upper limit of normal [ULN]) beginning 1 to 4 weeks after AT132 administration (Shieh, 2023). Liver findings included intrahepatocellular and canalicular cholestasis, periportal and bile ductular reaction, secondary fibrosis, and notable lack of prominent liver parenchymal inflammatory cellular infiltrates (Shieh, 2020).
- **Myocardial events:**
 - *Acute cardiac risks:* Acute myocardial events manifested as myocarditis and increases in troponins. In Study ATX-MTM-002, variable increases in troponin levels after AT132 administration were commonly observed. Two subjects experienced SAEs of myocarditis: 1 subject who received the 1.0×10^{14} vg/kg dose and 1 subject who received the 3.0×10^{14} vg/kg dose. Prolonged prednisolone administration plus addition of other immunosuppressive medications were used for treatment of myocarditis.

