4.4 Prophylaxis with Glucocorticoids

Subjects will be administered a course of concomitant glucocorticoid therapy commencing 1 day prior to AT132 dosing, and continuing for a period of approximately 8 weeks, then tapering from the original dose over 8 weeks per Investigator discretion. This is intended to prevent any immune-mediated hepatic injury, which has been observed in subjects who have received systemic AAV gene therapy (discussed in [Section 6.5.2](#)). For subjects weighing < 60 kg, the dose will be 1 mg/kg prednisolone orally daily for 8 weeks, then tapered down for 8 weeks per

Investigator discretion. For subjects weighing ≥ 60 kg, the dose will be 60 mg prednisolone orally daily for 8 weeks, then tapered down for 8 weeks per Investigator discretion. Investigators should closely monitor all liver function (see [Appendix 1](#)) results throughout the study. Management of prophylactic prednisolone dosing in the setting of abnormal liver function test (LFT) results is discussed in [Section 4.6](#).

The suggested prednisolone tapering regimen for subjects weighing < 60 kg is:

- Weeks 1 to 8: 1.0 mg/kg/day
- Weeks 8 to 9: 0.75 mg/kg/day
- Weeks 9 to 10: 0.50 mg/kg/day
- Weeks 10 to 11: 0.25 mg/kg/day
- Weeks 11 to 12: 0.125 mg/kg/day
- Weeks 13 to 14: 0.0625 mg/kg/day
- Weeks 15 to 16: 0.03125 mg/kg/day
- Week 16: Off

The suggested prednisolone tapering regimen for subjects weighing ≥ 60 kg is:

- Weeks 1 to 8: 60 mg/day
- Weeks 8 to 9: 45 mg/day
- Weeks 9 to 10: 30 mg/day
- Weeks 10 to 11: 15 mg/day
- Weeks 11 to 12: 7.5 mg/day
- Weeks 13 to 14: 3.75 mg/day
- Weeks 15 to 16: 1.875 mg/day
- Week 16: Off

Tapering duration may be altered and/or supplemental administration of IV steroids (eg, methylprednisolone) or other immunosuppressive regimens may be considered in cases of potential malabsorption of oral medications.

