4.6.2.3 Risk Management of Hepatobiliary Toxicity

Management of subjects with hepatobiliary toxicity will depend on the interpretation of all available clinical data.

- The site hepatologist must be actively involved in any case where the LFTs are higher than the values listed in the routine surveillance guidelines ([Section 4.6.2.2](#)). Management in this setting may be highly variable and may require additional diagnostic testing and/or alteration of the existing immunosuppressive regimen.

- In cases where the LFTs are rising but are within the values listed in the routine surveillance guidelines ([Section 4.6.2.2](#)) and the subject is on prophylactic glucocorticoids, prednisolone adjustments may be made at the discretion of the Investigator based on the stage of prophylaxis (steady dose or tapering). For cases refractory to prednisolone adjustment, consult the Medical Monitor.
- In cases where the ALT or AST are rising but are within the values listed in the routine surveillance guidelines ([Section 4.6.2.2](#)) and the subject is not on prophylactic glucocorticoids, consultation with the Medical Monitor is recommended, and management may require additional diagnostic testing and/or treatment with immunosuppressive agents
- In cases of clinically significant elevated LFTs and/or elevated CK that in the Investigator's judgment may be related to T cell responses, repeat cytokine panel and IFN- γ ELISpot response testing is suggested
- Following the Week 4 complement panel collection, in cases of clinically significant elevations in LFTs (and/or thrombocytopenia, acute renal insufficiency, or anemia), repeat complement panel testing is suggested

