4.10.3 Imputation Rules for Incomplete Dates

In case of missing or partial start and stop dates for concomitant medications, the following rules will be used:

If the start date is missing or partial:

- if the month is missing, use January
- if the day is missing, use the first day of the month under consideration
- if the year is missing, use year of the informed consent date
- if the entire date is missing, use informed consent date

If the stop date is missing or partial:

- if the month is missing, use December
- if the day is missing, use the last day of the month under consideration
- if the year or the entire date is missing, set the stop date to December 31st, 2099

If the imputed start date is after the stop date, then the imputed start date will be 1 day prior to the stop date.

For AEs, a missing or incomplete onset date will be imputed according to the following conventions.

If an onset date is missing or only the year is known, the imputed onset date will be the date of first dose of study drug.

If only the year is known for the AE onset date, the imputed onset date will be the latest of the following non-missing dates:

- Date of first dose of study drug

- January 1 of the year of AE onset date

If only the month and year is known for the onset date, set the surrogate onset date to the first day of that month and then apply the following rules.

- If the month and year of the onset date is prior to the month and year of the first dose of study drug, then the surrogate onset date will be the imputed onset date.
- If the month and year of the onset date is on or after the month and year of the first dose of study drug, then the imputed onset date will be the **latest** of the following non-missing dates:
 - Date of first dose of study drug
 - Surrogate onset date
 - If the imputed onset date is after the adverse event end date, the imputed onset date will be the same as the adverse event end date.

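### The SAP's count of days on the protocol steroid dose is elapsed time to the first dose reduction, with no check of the dose given, and taper duration has no end-date rule

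*SAP*

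**What the plan says.** SAP 4.2.6 plans a steroid table by AT132 dose level and overall, with two rows.

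- The first is "Total days on protocol-specified glucocorticoid dose regimen", with the regimen spelled out as 1 mg/kg daily below 60 kg and 60 mg daily from 60 kg. Its formula is "prior to taper (day prior to taper start date – Day -1 date + 1". Taper start is the first glucocorticoid record whose daily amount "is less than the (frequency)*(dose) value for the initial glucocorticoid record in the dataset".
- The second is "Duration of Taper". It is named without a formula or an end date.

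The only rule for missing stop dates of concomitant medications is in SAP 4.10.3: "if the year or the entire date is missing, set the stop date to December 31st, 2099". No cap is given.

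Protocol 4.4 sets the planned course below 60 kg as "Weeks 1 to 8: 1.0 mg/kg/day", starting on Day -1, then an 8-week taper. Protocol 4.6.2.3 allows departures when liver tests rise during prophylaxis: "prednisolone adjustments may be made at the discretion of the Investigator based on the stage of prophylaxis (steady dose or tapering". Protocol 1.5 reports two serious myocarditis events and adds: "Prolonged prednisolone administration plus addition of other immunosuppressive medications were used for treatment of myocarditis".

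**The concern.** The label of the first row promises a count of days at a stated dose. The formula delivers the time from Day -1 to the first reduction below whatever the child started on. An increase is never a taper under the SAP's rule, so days at a raised dose before the first reduction are counted as protocol-dose days. So are days in a gap, or on an initial dose other than the protocol one. A child who never has a record below the initial one has no taper start, and no rule says what happens to that child in the table.

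The row is therefore accurate where dosing went to plan and unreliable where it did not. Hepatobiliary and myocardial toxicity are identified risks in this trial, and steroid changes are part of their management. A reader using the table to see how much treatment followed the planned prophylaxis could take escalated treatment for a long course at the planned dose. SAP version 3.0 dropped the total-dose statistics, so these two rows are the only numerical steroid summary that 4.2.6 names.

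**Working it through.** **Inputs.** The formula and taper rule come from SAP 4.2.6, the 8-week full-dose period and 8-week taper from Protocol 4.4, and the stop-date rule from SAP 4.10.3. The documents contain no individual steroid records, so every course below is constructed for illustration. Neither document states an expected value for either row, so there is no plan figure to reproduce.

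**Step 1: what the formula returns.** Day -1 is the day before Day 1, with no Day 0. If taper starts on Day T, the interval holds Day -1 plus Days 1 to T − 1, which is 1 + (T − 1) = T days. The formula always returns the study-day number of taper start, whatever was given before it.

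**Step 2: formula against days at the protocol dose before taper start.**

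| Constructed course | Taper start | Formula | Days at protocol dose |
|---|---|---|---|
| Protocol dose, Day -1 to Day 56 | Day 57 | 57 | 1 + 56 = 57 |
| Protocol dose to Day 28, doubled Days 29–140 | Day 141 | 141 | 1 + 28 = 29 |
| Protocol dose to Day 28, doubled Days 29–84, protocol dose Days 85–112 | Day 113 | 113 | 29 + 28 = 57 |
| Protocol dose to Day 28, higher-dose IV course replacing oral Days 29–42, protocol dose Days 43–70 | Day 71 | 71 | 29 + 28 = 57 |
| Protocol dose to Day 28, raised Days 29–365 | Day 366 | 366 | 29 |
| Initial dose twice or half the protocol dose, held to Day 56 | Day 57 | 57 | 0 |
| Protocol dose to Day 56, no later record below it | none | no value | 57 |

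**Step 3: effect on a group mean.** Protocol 1.4.2 gives 17 high-dose and 6 low-dose children at the cut-off of 08 July 2020; I use these only to set the scale. One child with 141 instead of 29 adds 112/17 = 6.6 days to a mean of 17, or 112/6 = 18.7 days to a mean of 6, against a planned 57.

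**Step 4: taper duration, conditional on a reading of the SAP.** Suppose it were programmed as imputed stop date minus taper start plus 1, and one child's stop date were missing or the steroid ongoing.

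- Assumed taper start 1 December 2021: 28,520 days to 31 December 2099.
- Assumed taper start 1 November 2017: 30,011 days.
- Planned taper: 8 × 7 = 56 days.
- Shift in the mean of 17 children: (28,520 − 56)/17 = 1,674 to (30,011 − 56)/17 = 1,762 days.

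The median would barely move. The first row uses no stop date, so the 2099 rule changes it by 0 days.

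**The case against.** The strongest answer is that this is one row of a descriptive table. Steroid exposure is not a listed endpoint, SAP section 2 rules out hypothesis testing, and what each child received can be seen elsewhere. SAP 4.2.6 provides a listing of all glucocorticoid administration, and SAP 4.6.1 commits to swimmer plots showing steroid dose and duration alongside events of special interest. A child with no taper still appears in both. The formula is exact for an uncomplicated course and unaffected by toxicity managed after the taper began. An oral protocol dose with an IV supplement on top is arguably still the protocol dose; only a course that replaces it is miscounted. All of that stands and limits the point. It does not make the row measure what its label says.

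It can also be said that the 2099 date is there to classify medications as previous or concomitant, where it is harmless, and that a maximum near 30,000 days would be noticed, because SAP 4.1 reports minimum and maximum. That is probably the intent. The SAP does not say so, and it leaves the taper row without any end-date rule, whereas duration on study in SAP 4.2.7 ends at last follow-up or discontinuation.

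Three stronger readings might be inferred and are not supported.

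- The 2099 date does not corrupt the count of protocol-dose days, because that formula never uses a stop date.
- Steroid exposure is not misreported throughout for children with toxicity. One row is mislabelled and one is undefined.
- The child described in Protocol 1.5 with more than 3 years of immunosuppression cannot be used to size the error. The text does not say that the drug was a glucocorticoid throughout, and gives neither the steroid dose nor the AT132 dose group.

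**Conclusion.** The point holds in a limited form. The first row carries a stated formula that gives a wrong figure for its own label whenever dosing before the first reduction was raised, interrupted or started off the protocol level. The illustrations run from 14 days too many (71 against 57) to 337 (366 against 29). The row gives no value where no reduction is recorded.

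The number of children affected is unknown. The protocol shows that adjustments were allowed and that prednisolone was prolonged for myocarditis. It does not show whose dose was raised before taper, and prolongation at an unchanged protocol dose is counted correctly. Protocol 1.5 reports four fatal outcomes involving hepatobiliary failure, without saying whether any came before a dose reduction.

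The taper-duration problem is separate and conditional. It arises only if the 2099 imputation is carried into a duration the SAP leaves undefined, and only for an ongoing or missing stop date. No efficacy result depends on either row.

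**What to change.** Amend SAP 4.2.6 in three places and SAP 4.10.3 in one.

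- **First row.** Either count only days whose recorded daily dose equals the protocol-specified dose, showing days above it separately, or keep the formula and rename the row *days from Day -1 to first reduction below the initial dose*. Renaming is the smallest sufficient change; the count answers the question the present label asks.
- **No taper.** Report the number of children with no record below the initial dose in each dose group. Count them to death, last contact or data cut-off and flag them as censored.
- **Taper duration.** Give it a formula, with its end capped in the same way.
- **SAP 4.10.3.** State that 31 December 2099 is never used in a duration.

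The cost is SAP wording and programming on concomitant-medication data already collected. SAP 1.2 plans a final database lock after all participants have completed the study, so the change can be in place for the final analysis at the latest.

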4.2.7 Extent of Exposure

Participants' duration on study will be summarized descriptively for the SAF both as a continuous variable and by counts and percentages for the following categories:

- < 3 months
- 3 – < 6 months
- 6 – < 12 months
- 1 – < 2 years
- 2 – < 5 years
- 5 – < 7 years
- 7 – < 10 years
- 10 + years

Duration on study is defined as:

$$\frac{(\max(\text{Date of last day of follow up, date of discontinuation}) - \text{date of dosing} + 1)}{365.25}$$

The information on drug dosing and study duration will be presented in a listing.

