3.7 Start and End of Study Definitions

First act of recruitment

The study start date is the date on which the clinical study will be open for recruitment of participants. The first act of recruitment is the date the first participant signs the informed consent form (ICF) and will be the study start date.

End of study

The end of the study is defined as the last visit or assessment shown in schedule of assessments ([Section 5.6](#)) for the last participant in the study. A participant is considered to have completed the study if the participant has completed all periods of the study including the last assessment shown in the schedule of assessments.

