- ^{bb} Subjects will be administered a course of glucocorticoid therapy commencing Day -1 and continuing for a period of 16 weeks as a preventative measure for immune-mediated hepatic injury. For subjects weighing < 60 kg, the dose will be 1 mg/kg prednisolone orally daily for 8 weeks, then tapered down for 8 weeks per Investigator discretion. For subjects weighing ≥ 60 kg, the dose will be 60 mg prednisolone orally daily for 8 weeks, then tapered down for 8 weeks per Investigator discretion.
- ^{cc} Ursodiol to be dosed at 20 mg/kg/day (divided either BID or TID at the Investigator's discretion) to Week 12 and at the Investigator's discretion thereafter.
- ^{dd} Viral shedding will be assessed on samples of saliva (swab), stool, and urine (diaper collection or urine bag). Collection of each sample type will begin on Day 1 and will continue until each sample type has 3 consecutive data points at or below the limit of detection (BLOD). Sponsor will notify site when collection can cease. Not conducted at Week 10 or 14.
- ^{ee} Subjects in Germany will not have a wrist X-ray. After the Week 48 visit, wrist X-ray only needs to be performed annually thereafter (Month 24, Month 36). As of protocol v12, the wrist X-ray assessment will no longer be collected at Month 48 visit onward.
- ^{ff} As of protocol v12, these assessments will no longer be collected at Month 48 visit onward.

5.6 Schedule of Events for Subjects Treated with AT132: Month 72 (Year 6) – Month 120 (Year 10) (End of Study)

Study Phase/Visit	Month 72	Month 84	Month 96	Month 108	Month 120
Study Day	2190	2555	2920	3285	3650
Visit Window (days)	±60	±60	±60	±60	±60
Physical Examination ^a	X	X	X	X	X
Ventilator Dependence Questionnaire ^b	X	X	X	X	X
Samples for:	X	X	X	X	X
Safety labs (hematology) (central lab) ^{c,d}	X	X	X	X	X
Safety labs (chemistry) (central lab) ^{d,e,f,g} Comprehensive metabolic profile ALT, AST, Total and direct bilirubin, GGT Serum bile acids, total (fasting preferred) PTT and PT/INR Troponin I and T CK Alpha fetoprotein	X	X	X	X	X
Liver ultrasound (local) ^f	X	X	X	X	X
Motor milestone assessments ^h	X	X	X	X	X
ACEND	X	X	X	X	X
Clinical global impression scales ⁱ	X	X	X	X	X
Swallowing questionnaire	X	X	X	X	X
Secretions management assessment ^j	X	X	X	X	X
AEs/concomitant medications	X	X	X	X	X

NOTE: Long-term follow-up visits and/or assessments after the 5-year (Month 60) visit can be done remotely per discretion of investigator in consultation with Medical Monitor.

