e. Previously referred to as 1.0 and 3.0×10^{14} vg/kg. The 1.0×10^{14} vg/kg and 3.0×10^{14} vg/kg dose levels based on the 1st generation titer method equate to 1.3×10^{14} vg/kg and 3.0×10^{14} vg/kg, respectively, based on an analysis of all historical Study 002 drug product lots using the 2nd generation vg titer assay.

Source: Data on file.

Two database locks are planned for this clinical study. The first database lock is intended for will occur after all ongoing participants complete the Week 24 visit and prior to all participants completing the 10-year follow-up period or withdrawing. The second (final) database lock will occur after all participants have completed the study.

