4.4.2.2.8 Survival

This endpoint will be summarized for low dose and the high dose groups separately for all participants in the FAS. Kaplan-Meier plots of time from the dosing date to event will be provided. In addition, the estimated survival rate at the following time-points will be presented by dose level group:

- 3 months
- 6 months
- 1 year
- 2 years
- 5 years
- 10 years

For this analysis, the date of a participant's death is considered the time of an event. Survival status should be assessed at each visit until the participant withdraws consent or completes the study. If the participant misses a visit or withdraws for a reason other than withdrawal of consent or death, the site should contact the parent(s)/LAR(s) to ascertain if the participant is

alive. For participants who withdraw from the study, the participant should be contacted every 6 months for 5 years after administration and every year for an additional 5 years (after the 5-year follow-up through 10-years follow-up) to assess for survival. If not alive, the cause and date of death should be requested and recorded.

Participants will be censored at the last known date/time of contact.

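### A child who finishes the study on the scheduled Year 10 day is tabulated as under 10 years on study and may be censored just before the 10-year survival landmark

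*SAP*

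**What the plan says.** SAP 4.2.7 (Extent of Exposure) says that "duration on study will be summarized descriptively for the SAF both as a continuous variable and by counts and percentages for the following categories". The list ends with '7 – < 10 years' and '10 + years'. Duration runs from dosing to the later of two dates, "Date of last day of follow up, date of discontinuation", counted inclusively (plus one day) and divided by 365.25.

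The heading of Protocol 5.6 identifies the last visit as "Month 120 (Year 10) (End of Study"). The table beneath it puts that visit on Study Day 3650 with a window of ±60 days. Protocol 3.7 adds: "The end of the study is defined as the last visit or assessment shown in schedule of assessments". SAP Tables 9 and 10 also use Day 3650 for Month 120, and for the assessments still collected at Month 120 they generally assign data from Day 3468 onward to that visit.

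For survival, SAP 4.4.2.2.8 measures time from dosing and says "the estimated survival rate at the following time-points will be presented by dose level group"; the last point listed is 10 years. Its censoring rule is "Participants will be censored at the last known date/time of contact". No conversion from years to days is given. SAP 4.2.1 has a disposition row for completing 10 years of follow-up, also without a day definition. On timing, SAP 1.2 says: "The second (final) database lock will occur after all participants have completed the study".

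**The concern.** The visit schedule counts a year as 365 days and the exposure derivation counts it as 365.25. Over ten years the two differ by 2.5 days, and a band boundary and a survival landmark both fall inside that gap. One child could therefore be a study completer in the disposition table, have data under Month 120 in the by-visit tables, and still appear in the exposure table as followed for less than 10 years.

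Later contact is not planned. Adverse event collection stops when the subject completes or withdraws (Protocol 6.1.3.2), and survival status is assessed only until withdrawal of consent or completion (SAP 4.4.2.2.8). The end date in the formula will therefore usually be the Month 120 visit. At stake is how the 10-year follow-up is described: how many children appear to have reached 10 years, and whether the 10-year survival rate by dose has anyone behind it.

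**Working it through.** **Inputs**
- Years on study = (last date − dosing date + 1)/365.25 (SAP 4.2.7).
- Dosing is Day 1 (Protocol 5.4; SAP Table 9), so a last contact on Study Day d gives an inclusive count of d days.
- Final visit: Day 3650 ± 60 (Protocol 5.6).

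**1. Reproduce the scheduled day.** 10 × 365 = 3650. Years 6 to 9 reproduce in the same way: 2190, 2555, 2920 and 3285. The schedule uses 365-day years.

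**2. Find where the top band starts.** 10 × 365.25 = 3652.5 days.
- Day 3650: 3650/365.25 = 9.993, so '7 – < 10 years'
- Day 3652: 3652/365.25 = 9.9986, so '7 – < 10 years'
- Day 3653: 3653/365.25 = 10.0014, so '10 + years'

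**3. Apply this to the whole window.** Days 3590 to 3710 are 3710 − 3590 + 1 = 121 days. Days 3590 to 3652 are 63 days and fall short; Days 3653 to 3710 are 58 days and reach the top band. 63/121 = 52.1%. All 121 days comply with the protocol.

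**4. Check survival at 10 years for a last contact on Day 3650.** The SAP gives no conversion here, so three year lengths were tried, each with elapsed days (3649) and with the inclusive count (3650).
- 365.25-day year (3652.5 days): censored before 10 years on both counts.
- Calendar year: for dosing dates from June 2017 to the end of 2021 the tenth anniversary is 3652 or 3653 elapsed days after dosing. Day 3650 falls 3 or 4 days earlier, so the child is censored first on both counts.
- 365-day year (3650 days): censored first on elapsed days, still at risk on the inclusive count.

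The child is censored before the landmark in five of six cases. The other year conversion in the SAP, the hospitalization rate in 4.6.2.5.3, also uses 365.25.

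**5. Illustrate the scale, using inferred counts.** Protocol 1.4.2 reports 6 low-dose and 17 high-dose children at the July 2020 cutoff. Three controls were then undosed (Protocol 3.1) and two stayed undosed (SAP 1.3), which implies 6 + (3 − 2) = 7 low and 17 high, 24 in all. Protocol 1.5 reports deaths in 1 low-dose and 3 high-dose children, leaving at most 6 + 14 = 20 possible completers. Assume no other losses and last contacts spread evenly over the window:
- tabulated below 10 years: 20 × 0.521 = 10.4
- still at risk at 10 years (365.25-day year): 6 × 0.479 = 2.9 low, 14 × 0.479 = 6.7 high
- chance that no low-dose child is at risk: 0.521^6 = 2%

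If every last contact is on Day 3650 instead, all 20 are tabulated below 10 years and none is at risk at 3652.5 days.

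**The case against.** The exposure table reports elapsed time, and 9.993 years is less than 10. Completion has its own rows in SAP 4.2.1, and the exposure section also gives a continuous summary and a listing, so a careful reader would see 9.99. That is fair. What stands is that a band labelled in whole years, beside a final visit labelled Year 10, will split completers by where in the window they happened to be seen.

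The survival part is an inference, because SAP 4.4.2.2.8 gives no day conversion. A contact after the last visit, such as follow-up of an ongoing event, would also move the censoring date. The Kaplan-Meier value and its standard error change only at deaths. With no death between Day 3650 and the landmark, the practical risk is that the row rests on few or no children, or prints as not estimable.

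A reader might infer four stronger things that the documents do not support.
- *That every completer will appear below 10 years.* This needs every last contact by Day 3652. A visit 3 to 60 days late reaches the top band.
- *That the 2-, 5- and 7-year boundaries fail in the same way.* Months 24, 60 and 84 do fall just short (1.999, 4.997 and 6.995 years), but none is an end-of-study visit. A child who continues is not placed by them; they matter only if last follow-up falls near those marks.
- *That a 10-year landmark at the first database lock is an error.* One list of time points serves both locks, and unreached landmarks are ordinary with censored data. The documents give neither the first dosing date nor the lock date.
- *That the 10-year survival estimate is wrong.* It may be thinly supported, but censoring alone does not bias it.

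**Conclusion.** The point holds for descriptive long-term reporting. The band result follows directly from the SAP formula and the protocol schedule, assuming no recorded contact after the final visit; it does not depend on how many children were dosed. The loss of children at risk at the 10-year survival landmark is conditional: it follows under the SAP's own 365.25-day year or a calendar year, but not under a 365-day year counted inclusively.

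The number of children affected cannot be fixed from the documents. About half of completers is an illustration that rests on evenly spread visits, and all of them is the case where every visit is on schedule. The counts of 7 and 17 are inferred, and replacement enrolment was permitted (Protocol 3.3.5), so they could differ. Further deaths or withdrawals would lower the number of completers. The Week 24 primary analysis is unaffected. The correction is worth making because final lock comes only after all participants complete, and the groups are small enough for a few days to decide whether anyone is at risk.

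**What to change.** - **SAP 4.2.7:** define the top band as 10 or more years, or completion of the Month 120 visit within its protocol window. Leave the other bands unchanged.
- **SAP 4.2.1:** use the same rule for the row on completing 10 years of follow-up.
- **SAP 4.4.2.2.8:** state the year-to-day conversion and print the number at risk at each landmark. Add a landmark at the lower edge of the Month 120 window, Day 3650 − 60 = Day 3590 (3590/365.25 = 9.83 years), on the same inclusive day count so that a child last seen that day is not censored one day early. Label it as such, and keep the 10-year row only where children remain at risk.

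Moving every band to the lower edge of its visit window is not advised. It would label 2495/365.25 = 6.83 years as 7 and count a withdrawal on Day 3600 as 10 or more years.

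The cost is SAP wording and a few lines of derivation code, with no new data. The downside is that the top band will include some completers with slightly less than 10.0 elapsed years, which needs a footnote.
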